5.3.2 Counselor Selection

Counselors will be recruited from participating CTP staff. The educational background, credentials, and experience of the clinical staff implementing the intervention will vary among CTPs. The term "counselor" as used in the present protocol does not imply a particular educational background or

credentialing. Rather, it is used as a shorthand term to refer to the clinical staff members administering the treatments.

5.3.2.1 Counselor Informed Consent

Counselors who volunteer to participate in this study and to be randomly selected to provide the STAGE-12 intervention will be asked to provide informed consent to indicate their willingness to participate. As part of the informed consent process, potential counselors will also be informed about their need to complete brief questionnaires and have their sessions recorded and reviewed by clinical supervisors.

5.3.2.2 Counselor Inclusion/Exclusion Criteria

Counselors and supervisors will be eligible for the protocol who:

- Are credentialed to provide these services in their respective regions,
- Are willing to participate in this study (and sign the informed consent form), complete the counselor assessments, learn and implement a manual guided STAGE-12 intervention and conform to any restrictions placed on TAU during the course of the study,
- Are willing to be randomly chosen to provide the STAGE-12 intervention,
- Are willing to have their sessions recorded and reviewed by a national expert, a supervisor, and/or independent rater; to participate in regular supervision sessions; and to complete process/adherence ratings for the duration of the protocol,
- Are approved by the CTP's administrative/supervisory staff as appropriate for the study (e.g., reliable, competent, likely to be with the CTP for the duration of the study),
- Have a working familiarity with 12 step recovery principles and the self-help groups that utilize them.

Counselors and supervisors will be excluded who:

Are unfamiliar with or negative toward a 12-step orientation to treatment.

All counselors who sign informed consent, meet the criteria above and are interested in participating in this protocol will be part of the pool of counselors from which two will be selected to provide the STAGE-12 intervention. Note that while specific training in the manual-driven TSF or Intensive Referral therapies excludes a counselor from the study, both counselors and supervisors will be required to have working familiarity with 12 step recovery principles and the 12-step recovery self help fellowships (AA, CA and/or NA). The counselor training for the STAGE-12 treatment is designed to work with counselors who are already familiar with the 12-step approach to recovery.

5.3.3 Participant Selection

5.3.3.1 Inclusion/Exclusion Criteria

Individuals will be eligible for the protocol who:

- Are 18 years of age or older
- Have been admitted to outpatient treatment at a participating CTP which has met the CTP inclusion criteria and have at least 5-8 weeks of outpatient treatment available with an intensity of 5-15 hours of treatment per week.
- Are able to provide consent for study procedures

- Are willing to provide information about their drug and alcohol use
- Have used cocaine, methamphetamine, amphetamine or other stimulant drugs within the past 60 days, or have been incarcerated within the past 60 days and had used stimulants during the 30 days prior to their incarceration
- Meet DSM-IV diagnostic criteria for current (within the last 6 months) abuse or dependence
 of cocaine, methamphetamine, amphetamine or other stimulant drugs as a primary or
 secondary drug of abuse
- Are willing to be randomly assigned to either STAGE-12 or treatment-as-usual and plan to be available for 6 months following randomization
- Are willing to be recorded during group and individual sessions

Individuals will be excluded who:

- Are in need of detoxification for opiate withdrawal (as judged by CTP clinical staff)
- Are seeking detoxification only, methadone maintenance treatment or residential/ inpatient treatment
- Have a medical or psychiatric condition that would, in the opinion of the clinic staff, make participation in this study hazardous
- Have been incarcerated more than 60 days within that past 90 days prior to baseline assessments
- Have pending legal action that would inhibit participation in the study
- Have previously enrolled in the study having met all eligibility criteria

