5.4.2 Primary Outcome Measures

The primary objective of this study is to examine the degree to which the STAGE-12 intervention integrated into treatment as usual (TAU) reduces the percent of days of stimulant drug use, particularly cocaine, methamphetamine, and amphetamine compared to TAU alone. As such, the primary outcome will be measured by participant self-report of stimulant use (cocaine, methamphetamine, and amphetamine) from baseline through the 6-month follow-up period, as assessed by the Substance Use Calendar. The primary measures will be collected as indicated in Table 1. Information regarding substances other than stimulants will be collected for secondary analysis.

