5.4.2.1 Substance Use Calendar

Self-reports of substance use will be assessed at each research visit via the Substance Use Calendar (SUC). Similar to the Timeline Follow-back procedure, the SUC is a calendar-based assessment in which individuals are asked to indicate whether they used cocaine, amphetamines, methamphetamines, opiates, alcohol, cannabis, or benzodiazepines on each day of the assessment period. The calendar is marked with both general (e.g., weekend days, holidays) and personal (e.g., birthday, anniversary, pay days) to help anchor the period and facilitate recall. The measure thus assesses substance use on a daily basis and allows flexible, continuous evaluation of substance use. The number of days used, either of any of the drugs or of each of them, is the variable derived from the SUC. Substance abusers' reports about their drug consumption using this method have been found to have high retest reliability, convergent and discriminate validity with other measures,

agreement with collateral informants' reports of patients' substance use, and agreement with results from urine assays (Fals-Stewart, O'Farrell, et al., 2000).

Secondary analyses will be conducted using percent of days of non-stimulant drug use and percent of days of use of any of the assessed drugs (stimulants and non-stimulants) as outcome variables. Days of 12-step meeting attendance will also be assessed using the Substance Use Calendar and will serve as one of the 12-step secondary outcome measures. Secondary measures will be collected as indicated in Table 1.

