5.4.3.1 Substance Use Indices

5.4.3.1.1 Urine Drug Screen

Although the Substance Use Calendar that will be used to assess days of drug use has demonstrated reliability and validity when compared against both collateral reports of drug use and urine toxicology results (Ehrman and Robbins 1994; Fals-Stewart, O'Farrell et al. 2000), and there is considerable evidence supporting the validity of self-reported substance abuse by drug users (Brown, Kranzler et al. 1992; Darke 1998), there continue to be concerns about the veracity of such self-reports (Magura and Kang 1996). Therefore, urine will be tested for the presence of cocaine, opiates, cannabis, benzodiazepines, methamphetamines, and amphetamines. Urine samples will be collected at the baseline interview, weeks 4 and 8 during the active intervention phase, and at each of the follow-up assessments.

Zanis et al (Zanis et al.1994) indicated that their results suggest that self-reports of drug use are more inclusive estimates of use than even weekly urinalysis. However, they as well as others (e.g., Fals-Stewart, et al., 2000; Del Boca and Noll, 2000) indicate that such self-reports were collected in the context of a setting in which urine results were also being collected and recommend continued use of urine collection. However, they do not necessarily advocate that urine results be viewed as a "gold standard." Rather, they point to the fact that one of the important conditions for obtaining valid selfreports of substance use is informing participants that their self-reports will be validated against an objective standard such as urines. This may enhance the accuracy of the participants' self-reports via a bogus pipeline effect (Jones and Sigall, 1970). Such effects occur when research participants provide information under conditions where they are led to believe that objective, external validation of their responses is available. The possibility that inaccuracies can be detected is hypothesized to increase the validity of verbal report data (Del Boca and Noll, 2000). This hypothesis was supported by the results of Hamid and colleagues (Harnid, Deren et al.1999), who found that the agreement between self-reported drug use and urine test results was significantly higher when the urine collection occurred prior to the self-report associated with timing of urine testing. Thus, urine screens will be conducted prior to the Substance Use Calendar to maximize the validity of the self-reports.

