10.3 Primary Outcomes

10.3.1 Hierarchical linear model

The primary outcome variable will be percent of days of stimulant use over the assessment window, based on Substance Use Calendar alone and assessed at baseline, weeks 4 and 8/end of treatment, 3 months and 6 months. This measure will be analyzed using hierarchical linear models. Specifically, the trajectory over time for an individual patient will be described by the Level-1 model

(1)
$$Y_{ijk} = X_i \varphi + \beta_{0ij} + \beta_{ij} t_{ik} + \varepsilon_{ijk}, \qquad k=1,..., n_i$$

where Y_{ijk} and ε_{ijk} are percent of days of stimulant use and error term of participant i at site j at post-baseline assessment k, β_{0ij} is the baseline percent of stimulant use, β_{ij} is the slope for participant i, t_{ik} is the number of weeks at post-baseline assessment k, n_i is the number of post-baseline assessments for participant i, which can differ between the participants reflecting attrition; X_i is a baseline variable describing whether participant i was court mandated for treatment ($X_i = 1$) vs. not court-mandated for treatment ($X_i = 0$).

The Level-2 model describes the slope for participant *i* as a function of the treatment arm:

(2)
$$\beta_{ii} = \alpha_{0i} + \alpha_1 I(STAGE-12) + b_{ii}$$

Here α_{0j} is the intercept for participants at the *j*th treatment site, α_1 is the effect of the STAGE-12 treatment, *I*(STAGE-12) is a 0-1 STAGE-12 treatment indicator and b_{ij} is a subject-specific random error term.

The Level-2 model also describes the baseline outcome measure for participant i:

$$\beta_{0ij} = \alpha_{00j} + b_{0ij}$$

Here α_{00j} is the intercept for participants at the *j*th treatment site and b_{0ij} is a subject-specific random error term.

The assumptions of the model are: a) $\mathbf{e}_{ij} = (\varepsilon_{ij1},...,\varepsilon_{ijn_i})^T$ are independent $N(0,\Sigma_i)$ where Σ_i depends in i only through its dimension, b) b_{ij} are independent $N(0, \sigma_b^2)$, uncorrelated with ε_{ijk} , c) b_{0ij} are independent $N(0, \sigma_0^2)$, uncorrelated with b_{ii} and ε_{ijk}

The primary analysis will evaluate the hypotheses H_0 : $\alpha_1 = 0$ vs. H_1 : $\alpha_1 \neq 0$ and rejection of the null hypothesis with $\alpha_1 < 0$ would indicate that STAGE-12 treatment reduces percent of days of substance use compared to TAU.

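### A stimulant other than cocaine, methamphetamine or amphetamine can qualify a person for entry, but the Substance Use Calendar as described does not ask about it and the primary outcome does not count it (minor)

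*Protocol*

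**What the plan says.** **Eligibility (Protocol 5.3.3.1).** The recent-use criterion accepts people who "Have used cocaine, methamphetamine, amphetamine or other stimulant drugs within the past 60 days". The DSM-IV criterion accepts current abuse or dependence "of cocaine, methamphetamine, amphetamine or other stimulant drugs as a primary or" secondary drug. Both can be met on a stimulant outside the three named.

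**Primary outcome (5.4.2).** The outcome is "participant self-report of stimulant use (cocaine, methamphetamine, and amphetamine) from baseline through the 6-month follow-up period". The same section words the objective more loosely, as whether STAGE-12 "reduces the percent of days of stimulant drug use, particularly cocaine, methamphetamine, and amphetamine compared to TAU alone".

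**Instrument (5.4.2.1).** On the Substance Use Calendar participants "indicate whether they used cocaine, amphetamines, methamphetamines, opiates, alcohol, cannabis, or benzodiazepines on each day of the assessment period". That is seven substance classes, three of them stimulants, and no entry for any other stimulant.

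**Analysis (10.3.1).** "The primary outcome variable will be percent of days of stimulant use over the assessment window, based on Substance Use Calendar alone".

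**Urine (5.4.3.1.1).** As a secondary measure, "urine will be tested for the presence of cocaine, opiates, cannabis, benzodiazepines, methamphetamines, and amphetamines". The section also rules out using urine results to adjust self-report.

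**The concern.** The drugs that let a person into the trial should be drugs that the primary outcome can register. Here the eligibility list is open-ended and the outcome list is closed. Section 4.1 states the objective for stimulant drugs without restriction, so the measure is narrower than both the population and the objective.

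A participant whose only stimulant is an unlisted one would give a flat record at zero in either arm and so carry no information on the slope effect tested in 10.3.1. A participant with mixed use would have part of that use missed. Because the gap lies in what is collected, a later analysis plan could not fill it.

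**Working it through.** **1. Setting the sections side by side**

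| Element | Section | Stimulants covered |
|---|---|---|
| Recent-use criterion | 5.3.3.1 | three named, plus any other |
| Diagnostic criterion | 5.3.3.1 | three named, plus any other |
| Objective | 4.1 | stimulants, not itemised |
| Primary outcome | 5.4.2 | three named |
| Calendar | 5.4.2.1 | three named |
| Analysis endpoint | 10.3.1 | stimulants, not itemised, calendar only |
| Urine panel | 5.4.3.1.1 | three named |

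The outcome can be no wider than its only source, the calendar. A day with use of an unlisted stimulant and none of the three is therefore entered as stimulant-free. The secondary calendar outcomes do not pick it up either: they cover non-stimulant drugs, or any drug among those the calendar assesses.

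**2. When a score of 0% arises**

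The outcome counts every day on which one of the three named drugs is used, whichever drug qualified the person. So 0% is recorded in a window only if none of the three was used in it. In the extreme case, use of an unlisted stimulant on 100% of days is recorded as 0%.

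**3. Illustrative size**

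The protocol states no figure for this group, so there is none to reproduce.

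Inputs from 10.6: two-sided alpha 0.05; difference 10 percentage points; SD 23.7; effect size 10/23.7 = 0.42; about 200 per arm; power approximately 85% at correlation 0.5 and 30% attrition.

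Assumption: a share q in both arms never uses a named stimulant during the trial, so registers no use and no treatment difference. The SD is held at 23.7.

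- Diluted difference = 10(1 − q); diluted effect size = 0.42(1 − q).
- At 85% power the standardised signal is 1.960 + 1.036 = 2.996.
- Diluted power = Φ(2.996(1 − q) − 1.960).

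| Assumed q | Difference (points) | Effect size | Argument of Φ | Power |
|---|---|---|---|---|
| 0% | 10.0 | 0.420 | 1.036 | 85.0% |
| 1% | 9.9 | 0.416 | 1.006 | 84.3% |
| 2% | 9.8 | 0.412 | 0.976 | 83.6% |
| 5% | 9.5 | 0.399 | 0.886 | 81.2% |
| 10% | 9.0 | 0.378 | 0.736 | 76.9% |

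Power reaches the 80% design target when 2.996(1 − q) = 1.960 + 0.842 = 2.802, that is 1 − q = 0.935, or q of about 6.5%.

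**The case against.** **The outcome wording is not fully closed.** The objective in 5.4.2 highlights the three drugs without excluding others, and 4.1 and 10.3.1 speak of stimulants generally. This stands as a reading of intent. It does not restore days that the calendar never asks about, and it shows that 5.4.2 is at odds with itself.

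**The form itself is not shown.** The missing entry is inferred from one descriptive sentence, and the protocol does not say how broadly the amphetamines entry is to be read. That is fair. The point therefore concerns the calendar as described. A broad reading would shrink the gap, but eligibility lists other stimulants in addition to amphetamine.

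**Other measures may catch some of this use.** The ASI-Lite records days of drug use over 30 days, and the Substance Use Events form records worsening of drug use. Both may help descriptively. Neither feeds the primary endpoint, and Table 1 schedules the ASI-Lite only at baseline, 3 months and 6 months.

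**The group is probably small.** The only contrast by drug type in the protocol is cocaine versus methamphetamine (10.4.4.1.4), and even at an assumed 5% the power stays above 80%. This stands and is why the point is minor. The planned blinded variance check (10.7) examines spread, so it would not reveal a diluted difference.

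**A stronger reading is tempting.** A reader might infer that everyone who qualifies on another stimulant scores 0% whatever they do. The documents do not support that, because any use of a named drug still counts. A reader might also infer that moving from cocaine to another stimulant would produce a false benefit for STAGE-12. Such a person would indeed be recorded as improved, but nothing indicates how often this happens, and a false difference would need it to differ between arms.

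**Conclusion.** The mismatch is real and no section closes it: a stimulant outside the three named can admit a person, yet days on which it is the only stimulant used are recorded as free of stimulant use. The consequence is limited. Randomisation is central and stratified, and the qualifying drug is a baseline feature, so such participants fall in either arm by chance. The expected effect is dilution, and no bias between arms is shown.

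The power loss is 0.7 points at 1%, 1.4 at 2% and 3.8 at 5%. These figures rest on assumed shares, on complete non-registration for the affected group and on an unchanged SD. Severity is minor: the case rests on matching the endpoint to the eligible population and the objective more than on power.

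**What to change.** Add an other-stimulant entry to the Substance Use Calendar and its eCRF, name it in 5.4.2.1, and state in 5.4.2 and 10.3.1 that it counts toward the primary outcome. Align the two descriptions within 5.4.2 at the same time. Eligibility, objective and endpoint then cover the same drugs.

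The cost is one more item per calendar day, one eCRF field and a sentence in each section. The model and the sample size need no change. If the calendar form already carries such an entry, correcting the text is enough.

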5.4 Outcome Measures and Assessments

In selecting assessment measures and the timing of their administration, an attempt was made to balance the amount of assessment involved from baseline through the active intervention period and the follow-up points against the desire for adequate coverage of relevant assessment domains (Gastfriend, Donovan et al. 2005). Concerns exist about both assessment burden for participants and potential assessment reactivity (Clifford and Maisto 2000; Epstein, Drapkin et al. 2005); that is, the frequency and duration of the assessments may serve an unintended therapeutic effect that may reduce the differences across conditions. The Protocol Development Team is aware of and sensitive to both the potential relationship between increased client burden and participant attrition and potential "assessment effects." These concerns were taken into account in deciding the measures chosen for the client.

A listing of the measures, description of the domains covered by each, and the times at which they will be administered is found in Table 1.

Table 1: STAGE-12 Schedule of Assessments

Instrument/ Assessment	Est Time to Administer	Computer Administer (Participants)	Baseline Week 0	Week 1	Week 2	Week 3	Week 4	Week 5	Week 6	Week 7	Week 8/ End of	3 mo post- randomization	6 mo post- randomization
Informed Consent													
Informed Consent	15-30 min		Х				ornica con						
Administrative Forms													
Incl./Exclus- ion	5-10 min		Х			7,4							
Randomiza- tion	5 min		Х										
Visit Form*	2 min			X	Х	Х	X	X	X	X	X		
Visit Form (Research)	2 min		х		X (Stage 12 only)		x				x	x	x
					Pa	rticipant	Assessmen	t Instrumen	ts	•		•	
	Diagnostic, Med	dical, and Psycho	osocial Bacl	ground N	leasures	T		1	,	,			
CTN Demo- graphic Form	5 min		Х										
DSM-IV Checklist	20 min		Х										
Medical History	5-10 min		X										
Substance Use			1	T	I	I	T	1	1	I			
Substance Use Calendar (SUC)**	10-30 min		X (past 90 days)				Х				Х	Х	X
Addiction Severity Index - Lite (ASL) (with AUDIT-C)	45 min at baseline; 15 min at followup		×									Х	X
Alcohol Breathalyzer	2 min		х				х				Х	×	×
Urine Drug Screen	5 min		х				Х				Х	Х	Х
Fagerstrom Nicotine Dependence	5 min		х								Х	Х	Х

Instrument/ Assessment	Est Time to Administer	Computer Administer (Participants)	Baseline Week 0	Week 1	Week 2	Week 3	Week 4	Week 5	Week 6	Week 7	Week 8/ End of Treatment	3 mo post- randomization	6 mo post- randomization
Secondary Outc	omes: 12-Step	Involvement ar	nd Attendan	ce Measu	res								
Self-help Activities Question-naire (SHAQ)	5 min	Х	Х				Х				×	Х	Х
Predictors and N	Mediators: 12-8	Step Measures											
12-Step Experiences and Expecta- tions (TSEE)	3 min	Х	Х										
Survey of Readiness for Alcoholics Anonymous Participation (SYRAAP)	5 min	Х	Х								Х		
Short Understanding of Substance Abuse Scale (SUSS)	5 min	Х	Х										
Spiritual Involvement and Beliefs Scale – Revised (SIBS- R)	5 min	X	X								X		
Predictors and N	Mediators: Sub	stance-Related	Measures	•									
Drug Taking Confidence Questionnaire – 8 (DTCQ – 8)	3 min	Х	Х								х		
Self-Efficacy Questionnaire – Patient (SEQ- P)	3 min	Х	Х								Х		
Stages of Change Readiness & Treatment Eagerness Scale (SOCRATES)	5 min	Х	X								X		

Instrument/ Assessment	Est Time to Administer	Computer Administer (Participants)	Baseline Week 0	Week 1	Week 2	Week 3	Week 4	Week 5	Week 6	Week 7	Week 8/ End of Treatment	3 mo post- randomization	6 mo post- randomization
Treatment Pro	cess Measure	s											
Helping Alliance Questionnair e (HAQ-II)	5 min	Х			X (Stage 12 only)						X (Stage 12 only)		
Treatment Services Review (TSR) – 30 day abbreviated version	10 min		Х				х				Х	X	X
Participant Satisfaction Survey (PSS)	5 min	х									X (Stage 12 only)		
						Admin	istrative Fo	ms		•	•		
Adverse Events	10-15 min			To be colle	ected at an	y time after ran	domization						
Serious Adverse Events	10-15 min			To be colle	ected at an	y time after ran	domization						
Substance Use Events	10-15 min						х				Х	Х	Х
Protocol Violations	To be collecte	ed at any time dur	ing the study										
Study Termination		ed at any time trea ant terminates fror									ed for study week	8.	
Treatment Tracking Form***	10-15 min			Х	Х	Х	х	Х	X	X	Х		
		ıp sessions must b				·				 	·		
		ill only collect data								nber of days	will vary by partici	pant.	
*** Treatment	Fracking Form i	s not administered	d to participa	nts. Informa	ation is gatl	nered through o	clinic treatme	nt records					

Counselor Measures			
Instrument/Assessment	Time to Administer (in minutes)	Prior to Randomization	End of protocol participation
Counselor Informed Consent	~15	x	
Short Understanding of Substance Abuse Scale (SUSS)	5	х	
Clinician and Supervisor Survey (CSS)	15	х	
Addiction Counseling Self-Efficacy Scale (ACSES)	5	х	
Attitudes towards 12-Step Groups (ATSG)	5	х	
STAGE-12 Integration Goal Commitment	5	х	
Counselor/ Administrator Perceptions of Impact of Protocol Participation	5		х

